**PROTOCOL TITLE: Manual vs. custom knee study**

have fair comparison between the custom and manual instrumentation and prevent treatment bias and include all iterations.

Following randomization, they will undergo elective, primary knee replacement utilizing standard Medacta GMK Sphere implants. [name] or [name] will be the attending surgeon for all subjects. Subjects will be admitted to the orthopaedic service following total knee replacement for standard postoperative care. Postoperative follow-up appointments will be arranged at the standard time points: at three weeks and at six weeks. A standard postoperative radiograph will be obtained at 6 weeks using EOS, and the TKR implant alignment will be evaluated in the coronal, sagittal and axial planes. All TKR implant alignment measures for both the pre and post op radiographs will be done by the manufacturer of the EOS Imaging system since they have the technical expertise to perform the measurements. TKR implant alignment will be compared to the preoperative plan that was created using the preoperative CT.

Only 13 out of the total 20 patients currently enrolled in the study have undergone surgery. Upon approval from the IRB, we can randomize the remainder of enrolled patients and the remaining 60 to include the 4th arm. We feel that the addition of the 4th arm strengthens the study and dataset more so than the randomization bias weakens the study design. We are prepared to report this bias in publication.

The following data will be collected from each consented subject's chart: Name, MRN, date of surgery, name of surgeon, operative time, total blood loss, discharge hemoglobin data, hemoglobin delta between pre-op and morning after surgery, and total tourniquet time.

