**9. Procedures Involved**

Subjects will undergo standard of care preoperative low-dose, biplanar x-ray (EOS) and standard of care preoperative CT of the surgical extremity. All subjects' preoperative standard of care CT will be used for surgical planning of bony resection during total knee replacement. They will then be randomized in a single-blinded fashion into one of four groups: Group A, using customized instrumentation derived from preoperative CT for both the femoral and tibial preparation; Group B, using customized instrumentation derived from the preoperative CT for the femoral preparation and manual instrumentation for the tibial preparation; Group C, using manual instrumentation for both the femoral and tibial preparation; and Group D, using customized instrumentation derived from the preoperative CT for the tibial preparation and manual instrumentation for the femoral preparation. The 4th randomization arm is being added in order to

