**PROTOCOL TITLE: Manual vs. custom knee study**

transmitted securely using Box.com in a dicom format.

Secondary outcomes of operative time and intraoperative blood loss will be obtained from the medical record. Wilcoxon Rank-Sum test will be used to compare the coronal, sagittal, and axial alignment measurements between groups. Student's t-test will be used to compare the secondary outcome measures of operative time and intraoperative blood loss between groups.

A power analysis was performed to determine appropriate sample size for each group to determine a 1 degree difference in component alignment. Previous literature has noted standard deviation in axial alignment with custom instrumentation is 1.5 degrees. With a p-value of 0.05 and a power of 0.8, our power analysis determined that each group needed to include 25 subjects to be appropriately powered. The planned sample size of 28 subjects in each group was chosen to fulfill this power analysis.

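### Section 9 implies 80 patients against 112 elsewhere, and the plan sets neither an analysis rule nor an allocation ratio for Group D, which was added after at least 13 operations

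*Combined protocol and SAP*

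**What the plan says.** Section 9 (Procedures Involved) describes four groups: "They will then be randomized in a single-blinded fashion into one of four groups". Group D, custom tibial with manual femoral preparation, is a late addition, made to "have fair comparison between the custom and manual instrumentation and prevent treatment bias and include all iterations". On where the trial stood at that time, the section says "Only 13 out of the total 20 patients currently enrolled in the study have undergone surgery", and then "Upon approval from the IRB, we can randomize the remainder of enrolled patients and the remaining 60 to include the 4th arm". It acknowledges a randomisation bias from the change, judges the fourth arm worth it, and closes with "We are prepared to report this bias in publication".

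Sections 4 and 23 each give the number of subjects as 112. Section 11 does not print a total. It plans 28 in each group and says of the power analysis that "our power analysis determined that each group needed to include 25 subjects to be appropriately powered".

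For the analysis, Section 11 says "Wilcoxon Rank-Sum test will be used to compare the coronal, sagittal, and axial alignment measurements between groups", with t-tests for operative time and blood loss. It does not restrict or adjust by stage of the trial. No section gives an allocation ratio, before or after Group D opened.

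**The concern.** There are three gaps, all arising from the added arm.

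1. **The count.** Section 9 and Sections 4, 11 and 23 cannot all be right about how many patients are still to come. The total sets the size of every arm.
2. **The analysis.** Patients operated on before Group D existed had no chance of being assigned to it. Putting them into a comparison with D sets later patients against a mixture of earlier and later ones. If alignment drifted over the trial, the drift enters the D contrast. Promising to report the bias does not settle which patients the comparison uses, so that choice could be made after the results are seen.
3. **The allocation.** Groups A, B and C started ahead of D. Without a stated ratio, nothing ensures that D catches up to the planned 28.

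D is the arm added for the sake of a fair comparison, so its contrasts are the ones that most need a written rule.

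**Working it through.** **Total sample size**

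- Sections 4 and 23: 112. Section 11 with the four groups of Section 9: 4 × 28 = 112, which reproduces the stated total.
- Section 9: 20 + 60 = 80, or equally 13 operated + 7 not yet operated + 60 = 80.
- Gap: 112 − 80 = 32. To agree with 112, the number remaining must be 112 − 20 = 92.

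If 80 governed, arms would average 80/4 = 20, below the protocol's own minimum of 25. Two-sided t-test power for 1 degree with SD 1.5 (Section 11's inputs; two-sided is my assumption) would be 54% at 20 v 20, against 69% at 28 v 28. The 25 is used only as the protocol's stated minimum; the same calculation gives 64% at 25 v 25, which is a separate matter.

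**Allocation after Group D opened (total 112)**

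- Patients left after the first 13: 112 − 13 = 99. Equal split: 99/4 = 24.75 expected in D, short of 28.
- If all 20 enrolled patients were treated before D opened: 92/4 = 23.
- To bring D to 28: 99 − 28 = 71 for A, B and C together (13 early), or 92 − 28 = 64 (20 early).

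**Bias in contrasts with D if all patients are pooled**

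Assumptions: 28 per group; early patients split evenly over A, B and C; SD 1.5; a constant shift s in alignment between the early and late stages. The documents give no value for s, so a range is shown. Early share p = (early/3)/28; bias = p × s; type I error from the noncentral t with noncentrality bias / (1.5 × √(2/28)).

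| Early patients | Early share of A, B, C | Shift s | Bias | Type I error (t-test) |
|---|---|---|---|---|
| 13 | 4.33/28 = 15.5% | 0.5 degree | 0.08 degree | 5.4% |
| 13 | 15.5% | 1 degree | 0.15 degree | 6.7% |
| 20 | 6.67/28 = 23.8% | 0.5 degree | 0.12 degree | 6.0% |
| 20 | 23.8% | 1 degree | 0.24 degree | 9.0% |

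For the Wilcoxon test, which Section 11 specifies for alignment, simulation with 13 early patients gave 5.0–5.1% at 0.5 degree and 5.8–6.3% at 1 degree.

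**Price of using only patients randomised when D was open**

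- 13 early: each of A, B and C keeps 28 − 4.33 = 23.67. Power at 28 v 23.67 is about 65%.
- 20 early: 28 − 6.67 = 21.33. Power at 28 v 21.33 is about 62%.
- Both compare with 69% at 28 v 28.
- Mean squared error, 13 early, s = 0.5: all patients 2.25 × (2/28) + 0.077² = 0.167; concurrent only 2.25 × (1/28 + 1/23.67) = 0.175.
- Break-even shift = √[2.25 × (1/concurrent n − 1/28)] / p = 0.78 degree (13 early) or 0.67 degree (20 early). Below that, pooling gives the smaller mean squared error.

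**The case against.** The strongest reply is that little is at stake. The number 112 is stated twice and implied a third time, so the 60 looks like a leftover from a smaller target. The drift is hypothetical: the same two surgeons operate, the implant is the same, and one manufacturer makes all the measurements. In the 0.5-degree, 13-early case the Wilcoxon error rate hardly moves and pooling has the smaller mean squared error. Pre-specifying either analysis would remove the freedom to choose afterwards. The protocol is also open about the bias.

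Most of that stands, and it limits the size of the point. It does not supply the missing analysis rule or ratio, and it does not reconcile the two counts. The case for concurrent-only as the main analysis is that it compares patients who could all have been assigned to D. That is a reason of design, not of precision.

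Four stronger readings are tempting, and the documents do not support them:

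- *The trial will run at 54% power.* This follows only if 80 governs, which is the less supported total.
- *The late arm invalidates the D comparisons.* The plausible bias is a small fraction of the 1-degree target.
- *Comparisons among A, B and C are compromised too.* They are not, provided their mutual ratio stays the same across stages.
- *The trial does not record who could have been assigned to D.* Section 9's list, which includes "date of surgery, name of surgeon, operative time, total blood loss", covers only items taken from the chart. Randomisation records would normally be kept elsewhere, so their absence from that list proves nothing.

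**Conclusion.** The point holds at a modest size and should be corrected. The contradiction between 80 and 112 is in current procedure text and is certain; that 112 is the intended figure is likely but not stated. The lack of an analysis rule for contrasts with D is also certain. Its probable effect is small: 0.08 degree and about 5.4% type I error with 13 early patients and a 0.5-degree shift, rising to 0.24 degree and 9.0% in the most adverse case tabulated. These figures rest on an assumed shift, an even early split over A, B and C, and 28 per group. The number of early patients is at least 13; the text does not say whether the other 7 already held a three-arm assignment, so 20 is the upper case for those then enrolled. The allocation gap is concrete: under an equal split, D is not expected to reach 28 even with 112 patients.

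**What to change.** 1. Reconcile Section 9 with Sections 4, 11 and 23. If 112 is intended, change the 60 still to come to 92.
2. Keep the sentence "We are prepared to report this bias in publication" and add after it: *Comparisons with Group D, and any pooled custom-versus-manual comparison, use only patients randomised when Group D was available. Comparisons among A, B and C use all patients. An all-patients analysis of Group D contrasts is reported as a sensitivity analysis.* Note for each patient whether Group D was open at randomisation.
3. State the allocation ratio for the four-arm stage. Set it so that D reaches 28, and keep A:B:C as in the first stage even if those arms then end slightly off 28. For example, if the first-stage ratio was 1:1:1 and the 13 early patients fell 5/4/4, 71/3 = 23.67 more in each arm gives expected totals of 28.67, 27.67 and 27.67. Forcing each to exactly 28 would change the ratio between stages and bring the stage problem into the A, B and C comparisons.

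The cost is one number, one ratio, one short rule and one recorded item. The statistical price is power of about 65% (13 early) or 62% (20 early) instead of 69% for 1 degree in D contrasts, and a less precise estimate unless the stage shift exceeds about 0.67–0.78 degree. The sensitivity analysis keeps the pooled result in view.

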### 3. Inclusion and Exclusion Criteria

#### 3.1 INCLUSION CRITERIA:

- Radiographically confirmed diagnosis of osteoarthritis (OA)
- Failure of non-operative treatment for the diagnosis of symptomatic Osteoarthritis
- Age greater than 18 years
- Desire to proceed with elective TKR
- Completion of informed consent and signature of written consent form

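### The chart-data list omits age, sex and BMI, so balance on these factors cannot be described by arm or period, and operative time and blood loss cannot be adjusted for them

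*Combined protocol and SAP*

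**What the plan says.** Section 9 (Procedures Involved) lists the chart data in a single sentence. It opens "The following data will be collected from each consented subject's chart: Name, MRN, date of surgery, name of surgeon, operative time, total blood loss" and ends "discharge hemoglobin data, hemoglobin delta between pre-op and morning after surgery, and total tourniquet time". Age appears elsewhere only as an entry criterion in Section 3.1 ("Age greater than 18 years"), not as a recorded variable. Sex and BMI appear nowhere.

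Section 9 also explains that a fourth randomised group, Group D, is being added during the trial. On its timing: "Only 13 out of the total 20 patients currently enrolled in the study have undergone surgery", and "we can randomize the remainder of enrolled patients and the remaining 60 to include the 4th arm". The authors accept a cost: "We feel that the addition of the 4th arm strengthens the study and dataset more so than the randomization bias weakens the study design". They add: "We are prepared to report this bias in publication".

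Section 11 compares alignment between groups with the Wilcoxon rank-sum test, and the secondary outcomes of operative time and intraoperative blood loss with Student's t-test. It plans no covariates and no table of baseline characteristics. The planned size is 28 per group, 112 in all (Sections 4, 11 and 23).

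**The concern.** A trial that changes its allocation scheme part-way invites two questions: are the arms alike, and are the patients treated before the change like those treated after it? Age, sex and BMI are the usual first answer, and this list does not contain them. Arms of 28 are small enough for sizeable imbalances to arise by chance, and Section 9 describes no stratification of the randomisation.

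Operative time and blood loss may also vary with patient build and other patient factors. In an unadjusted t-test that variation stays in the error term, and without the fields it cannot be removed later. The gap also becomes harder to close with time, because Section 10 has identifiable data destroyed a year after the study is complete.

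**Working it through.** **1. Is the omission real?** The Section 9 list contains name, record number, surgery date, surgeon, operative time, blood loss, discharge haemoglobin, change in haemoglobin, and tourniquet time. No section adds a demographic variable or body size. The sentence is complete, so the gap is not explained by redaction or by text extraction.

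**2. What can the listed data show about the admitted bias?** The bias arises because nobody among the first 13 operated could have been allocated to Group D. The share of subjects affected depends on which total is used:
- against the stated 112: 13/112 = 12%, leaving 112 − 13 = 99 subjects with Group D open;
- against the total implied by Section 9, 20 + 60 = 80: 13/80 = 16%, leaving 80 − 13 = 67.

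Section 9 draws the line by whether surgery had taken place, so the surgery date separates the two periods. With surgeon also recorded, the trial can restrict to concurrent subjects, stratify by period and check the mix of surgeons. It cannot compare the periods on age, sex or BMI.

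**3. How large could an unseen imbalance be?** Inputs: 28 per group (Section 11) and an assumed prevalence of 50% for some binary characteristic. The SD of the difference in proportions between two arms is √(2 × 0.25/28) = 0.134, or about 13 percentage points. Differences of one to two SDs, 13 to 26 points, are therefore plausible by chance.

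**4. What could adjustment gain?** The plan gives no effect size, SD or power for operative time or blood loss, so there is no figure of its own to reproduce here. Its one sample-size calculation concerns alignment and does not enter this point. The following is an illustration only. Assumptions: a true difference of 0.6 SD, 28 per arm, two-sided 5% t-test, and covariates that explain a share R² of the outcome variance. Adjustment reduces the residual SD by the factor √(1 − R²), so the effective standardised difference is 0.6/√(1 − R²), and the equivalent unadjusted size is 28/(1 − R²) per arm.

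| R² | Effective difference (SD) | Power | Equivalent n per arm |
|---|---|---|---|
| 0 | 0.600 | 59.7% | 28 |
| 0.1 | 0.632 | 64.2% | 31 |
| 0.2 | 0.671 | 69.3% | 35 |
| 0.3 | 0.717 | 75.0% | 40 |

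These figures ignore the few degrees of freedom that the covariates use.

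**The case against.** A reader might infer that, without patient characteristics, the bias the authors promise to report cannot be examined at all. The documents do not support that. The bias is one of calendar time and allocation, and surgery date and surgeon are both on the list. The promise itself is to disclose the bias; it does not commit the authors to an analysis of covariate balance.

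It would also go too far to say that no patient-level baseline information exists. Alignment is measured before as well as after surgery ("All TKR implant alignment measures for both the pre and post op radiographs will be done by the manufacturer of the EOS Imaging system"), and a change in haemoglobin implies a preoperative value. The record number is collected, so other fields could be retrieved under an amended list while identifiers exist.

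The strongest objection is that adjustment is optional. Randomised comparisons among concurrent subjects are valid without it, and these outcomes are secondary and not the basis of the sample size. The power gains rest on an effect and R² values that the documents do not supply, and they would apply to almost any two-arm t-test. A model with only arm, age, sex and BMI would also miss the two collected variables closest to the problem, period and surgeon.

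All of that stands, and it limits the point to precision, chance imbalance and description. It does not remove the omission: followed as written, the protocol yields no table of age, sex or BMI by arm or period, and no means of adjusting for them.

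**Conclusion.** The point holds as a minor, inexpensive improvement. The chart list leaves out age, sex and BMI. Comparability on those three factors therefore cannot be described across arms or across the periods before and after Group D opened, and the secondary outcomes cannot be adjusted for them. The validity of unadjusted comparisons among concurrently randomised subjects is not in question.

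The 13 subjects operated on before Group D opened are 12% to 16% of the trial, depending on which total applies. The possible gain in power for a secondary outcome runs from about 4 to 15 percentage points (59.7% to 64.2% at the low end, 59.7% to 75.0% at the high end). That range is conditional on the assumed 0.6 SD effect, 28 per arm, and R² between 0.1 and 0.3. If the three factors explain little of the variance in these outcomes, the gain in precision is small and the descriptive benefit is what remains.

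**What to change.** - Add age, sex and BMI to the Section 9 chart list for every subject, including the 13 already operated, and extract them before identifiers are destroyed under Section 10.
- Prespecify a baseline table of these factors by arm and by period (before and after Group D opened).
- In Section 11, replace the t-test for operative time with a prespecified linear model containing arm, surgeon, randomisation period, age, sex and BMI. Fit the same model to blood loss as a supporting analysis.
- Limit comparisons with Group D to subjects randomised after it opened, at least as a sensitivity analysis.

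The cost is a minor protocol amendment, three routine chart fields per subject and a few degrees of freedom. No new visit, procedure or patient is needed.

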**10. Data and Specimen Banking**

All information regarding the nature of the proposed investigation provided to the investigator (with the exception of information required by law or regulations to be disclosed to the IRB, the subject, or the appropriate regulatory authority) will be kept in confidence by the principal investigator. All personal information will be treated as strictly confidential and not made publicly available. All records are stored in a locked filing cabinet and password protected computers which are accessed only by the Principal Investigator, Co-Investigator, and authorized study staff. All identifiable data will be destroyed a year after the study is complete.

**11. Data and Specimen Management**

The primary outcome measure of total knee arthroplasty component alignment will be measured on the postoperative EOS image obtained at the six week follow-up appointment. Alignment will be measured in the coronal, sagittal and axial planes and compared to the preoperative plan created with the preoperative CT. All TKR implant alignment measures for both the pre and post op radiographs will be done by the manufacturer of the EOS Imaging system. All radiographs sent to EOS Imaging will be fully de-identified and will be

**PROTOCOL TITLE: Manual vs. custom knee study**

transmitted securely using Box.com in a dicom format.

Secondary outcomes of operative time and intraoperative blood loss will be obtained from the medical record. Wilcoxon Rank-Sum test will be used to compare the coronal, sagittal, and axial alignment measurements between groups. Student's t-test will be used to compare the secondary outcome measures of operative time and intraoperative blood loss between groups.

A power analysis was performed to determine appropriate sample size for each group to determine a 1 degree difference in component alignment. Previous literature has noted standard deviation in axial alignment with custom instrumentation is 1.5 degrees. With a p-value of 0.05 and a power of 0.8, our power analysis determined that each group needed to include 25 subjects to be appropriately powered. The planned sample size of 28 subjects in each group was chosen to fulfill this power analysis.

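### Two surgeons operate and the surgeon is recorded, yet the planned tests ignore surgeon: they stay valid but forgo a nearly free gain in precision

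*Combined protocol and SAP*

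**What the plan says.** Section 9 (Procedures Involved) names two surgeons, one or other of whom "will be the attending surgeon for all subjects". The data to be taken from each chart include "name of surgeon, operative time, total blood loss". Allocation is described only in these terms: "They will then be randomized in a single-blinded fashion into one of four groups". No allocation method, blocking or stratification factor is given.

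Section 11 (Data and Specimen Management) states the analysis in two sentences. For the primary outcome, "Wilcoxon Rank-Sum test will be used to compare the coronal, sagittal, and axial alignment measurements between groups". For the secondary outcomes, "Student's t-test will be used to compare the secondary outcome measures of operative time and intraoperative blood loss between groups". Surgeon appears in neither, and nowhere else do the documents mention a covariate, a stratified test or a surgeon-by-group analysis.

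The sample size in Section 11 was set "to determine a 1 degree difference in component alignment", using a literature value in which the "standard deviation in axial alignment with custom instrumentation is 1.5 degrees". The plan does not say whether that SD includes variation between surgeons.

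**The concern.** The surgeon carries out the procedure being compared, and all the named outcomes (component alignment, operative time, blood loss) are products of the operation. If the two surgeons differ systematically on any of them, a test that ignores surgeon pays in two ways. The difference is counted as random error, which lowers power. And if one group happens to contain more of one surgeon's cases, part of the observed instrumentation difference belongs to the surgeon.

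Precision matters here because, on the plan's own inputs, two-sided power at 28 per group is already below the intended 0.80. The variable that could recover some of it is being collected anyway.

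**Working it through.** **Inputs from the documents.** Difference 1 degree, SD 1.5 degrees, alpha 0.05 (sidedness not stated), power 0.8, 25 per group required, 28 planned, four groups.

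**Inputs that must be assumed.** The mean difference *d* between surgeons and one surgeon's share *p* of the caseload. I use *p* = 0.5 and a range of *d* that starts near zero.

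**The plan's own figure.** n = 2(1.96 + 0.842)² × 1.5² / 1² = 35.3, so 36 per group two-sided (37 with the t distribution). One-sided, the normal formula gives 28. The stated 25 does not reproduce either way; that is a separate point. Two-sided t-test power at 28 per group is 0.688, the baseline below. (One-sided, on the normal approximation, it is 0.80.)

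**Power, if 1.5 is the total SD.** Surgeon contributes variance p(1 − p)d² = 0.25d². Adjustment leaves a residual SD of √(2.25 − 0.25d²).

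| Surgeon difference *d* (degrees) | Share of variance, 0.25d²/2.25 | Residual SD | Power at 28 per group |
|---|---|---|---|
| 0 | 0% | 1.500 | 0.688 |
| 0.3 | 1.0% | 1.492 | 0.692 |
| 0.5 | 2.8% | 1.479 | 0.700 |
| 0.67 | 5.0% | 1.462 | 0.710 |
| 1 | 11.1% | 1.414 | 0.738 |
| 1.34 | 20.0% | 1.342 | 0.782 |

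**Power, if 1.5 is the within-surgeon SD.** The unadjusted test then works with a larger SD, √(2.25 + 0.25d²). In a simulation of the planned rank-sum test (28 per group, even caseload, 40,000 runs), power was 0.66, 0.61 and 0.50 for *d* = 0, 1 and 2 degrees. A linear model with surgeon gave about 0.68 each time. About 2 points of each gap come from the type of test, since the gap is already there at *d* = 0. Type I error of the unadjusted rank-sum test was 0.046 to 0.048.

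**Chance imbalance, if randomisation is simple.** The difference between two groups of 28 in one surgeon's share has SD √(2 × 0.5 × 0.5 / 28) = 0.134. Its mean absolute value is about 0.798 × 0.134 = 0.107 (0.106 from the exact binomial), or about 11 percentage points. The gap is 20 points or more in about 14% of pairs.

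- Alignment: 0.106 × 1 = 0.11 degrees average shift per degree of surgeon difference.
- Operative time: if the surgeons differ by 20 minutes (assumption), 0.106 × 20 = 2.1 minutes.
- With an 80:20 caseload, the SD falls to √(2 × 0.8 × 0.2 / 28) = 0.107, and gaps of 20 points or more to about 6.5% of pairs.

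No SD is given for operative time or blood loss, so the power gain for those outcomes cannot be calculated.

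**The case against.** The strongest reply is that nothing here is an error. Under randomisation an unadjusted comparison is valid, and its p-value already allows for chance imbalance; the simulated type I error confirms this. That stands. A reader might infer from the absence of surgeon in the tests that the results would be biased or the false-positive rate inflated. The documents do not support that.

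The second reply is that the gain may be small. Alignment is compared with each patient's own CT-based preoperative plan (Sections 9 and 11), so differences between the surgeons in target alignment may largely cancel, leaving execution error. This also stands. To reach 20% of the variance, the surgeons' means would have to differ by about 1.34 degrees, more than the 1 degree instrumentation effect the trial is sized for. A surgeon effect is more plausible for operative time and blood loss, but those are secondary.

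Third, a reader might conclude that allocation was not stratified by surgeon. Section 9 is silent on the allocation method, so this cannot be inferred. Stratification that was used but not described would limit the imbalance, though an unadjusted test would still leave surgeon variance in the error term.

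One feature of this trial slightly favours adjustment. Group D was added after 13 enrolled patients had undergone surgery. If the surgeon mix changed over time, comparisons with Group D could carry more than chance imbalance. The documents do not say that it changed.

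**Conclusion.** The point holds as a missed improvement in precision, not as a flaw that invalidates the analysis. The facts are clear: two surgeons, surgeon recorded, and neither planned test using it. The size is not, because no between-surgeon difference or caseload split is given. With an even caseload and a total SD of 1.5 degrees, adjustment is worth about 1 percentage point of power or less if the surgeons differ by 0.5 degrees or less, about 5 points at 1 degree and about 9 at 1.34 degrees. The average shift from chance imbalance is about a tenth of whatever the surgeon difference is, and less with an uneven caseload.

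It would be too strong to say that adjustment makes the trial adequately powered. On the two-sided calculation, power stays below 0.80 at every surgeon difference in the table. The shortfall comes from the sample-size calculation and needs its own correction.

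**What to change.** In Section 11, replace the plain rank-sum test for alignment with a surgeon-stratified rank test (van Elteren). Analyse operative time and blood loss in a linear model with group and surgeon. If a single model for all four arms is adopted, include surgeon as a term in it. In Section 9, state the allocation method and, where feasible, stratify the list by surgeon for patients not yet randomised.

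The cost is a wording change, one degree of freedom in the linear model and a two-stratum list for the remaining patients. No new data and no extra patients are needed. Settling the adjustment now also avoids a choice made after the results are seen.
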